12.0 CRITERIA FOR THERAPEUTIC RESPONSE/OUTCOME ASSESSMENT

All patients will have their tumor measurements recorded at baseline and at the time of each MRI scan. Lesions must be measured in two dimensions. The dose of gadolinium must be held constant from scan to scan.

Because the first MRI obtained after radiotherapy often shows an increased pattern/area of enhancement of indeterminant significance this scan will not be used to assess response to therapy or to make a decision as to whether or not a patient remains on study. The first MRI after radiotherapy will be used as a new baseline scan for subsequent MRI assessments.

Complete response (CR) is the total disappearance of all measurable contrast enhancing tumor on two MRIs separated by at least 4 weeks. The patient must have no clinical neurologic deterioration or decrease in performance status. The patient must be off dexamethasone.

Partial response (PR) is at least a 50% reduction in the size of measurable contrast enhancement (the sum of the products of the greatest length and maximum width of all measurable lesions). No lesion may progress and no new lesions may appear. All PR should be confirmed by repeat MRI separated by at least 4 weeks. The dose of dexamethasone must be the same or lower than at baseline.

Stable disease (SD) exists when a patient fails to qualify for partial response or progressive disease.

IRB#: 05-079A(17)

Progressive disease (PD) is an increase of 25% or more in the size of any lesion or the appearance of a new site of tumor.

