9.2 Randomized adjuvant therapy

This therapy will begin 2- 4 weeks after the completion of radiotherapy and will last for a total of 6 cycles (1 cycle = 28 days). Patients will be randomized to receive dose dense or metronomic temozolomide on the basis of histology and KPS.

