10.0 EVALUATION DURING TREATMENT/INTERVENTION

During concurrent temozolomide and radiotherapy:

- CBC every week.
- Brief physical exam weekly by radiation oncology.
- Contrast enhanced MRI (including perfusion) at the completion of radiotherapy and prior to initiation of adjuvant therapy – this will be considered a new baseline MRI and all patients may continue to adjuvant temozolomide.

During adjuvant temozolomide:

- CBC every week
- Monthly exam
- Contrast enhanced MRI (including perfusion) after every 2 cycles of therapy patients with evidence of tumor progression as compared to the post radiotherapy MRI will be removed from the study.
- Monthly comprehensive chemistry panel.

During maintenance cis-retinoic acid:

- Approximately monthly exam for 6 months then approximately every 2-3 months thereafter.
- Monthly CBC, comprehensive chemistry panel and lipid panel.
- Contrast enhanced MRI (including perfusion) after every 2-3 cycles of therapy patients with evidence of tumor progression as compared to the post radiotherapy MRI will be removed from the study.

IRB#: 05-079 A(17)

MGMT analysis:

Unless MGMT analysis was already performed as part of routine care at MSKCC or an MSKCC designated laboratory, *MGMT* methylation analysis will be performed by real-time PCR using TaqMan machine via OncoMethylome Sciences SA. Ten paraffin slides (around 10 micron), heated or baked (maybe less than 65C) per patient will be required. DNA will then be isolated and modified for real-time PCR on modified DNA. The final result will be the relative ratio of *MGMT* methylation / beta-actin as compared with positive control coming with the DNA modification kit.

[name], (Project Coordinator NA) should be contacted before any shipment. Samples must arrive during business hours from Monday through Friday and shipped overnight to:

OncoMethylome Sciences SA

Attn: [name]

[name]

[name]

[name]

[contact]

Contact information for [name]:

[contact]

[contact]

Email: [contact]

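### Progression is judged against the post-radiotherapy MRI, not the smallest size since, so PFS can be dated late when a lesion shrinks and regrows at the same site

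*Combined protocol and SAP*

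**What the plan says.** Section 12.0 says that progressive disease "is an increase of 25% or more in the size of any lesion or the appearance of a new site of tumor". That sentence does not say which scan the increase is measured from. Three other places supply the reference:

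- Section 12.0: "The first MRI after radiotherapy will be used as a new baseline scan for subsequent MRI assessments".
- Section 10.0, once for adjuvant temozolomide and once for maintenance: "patients with evidence of tumor progression as compared to the post radiotherapy MRI will be removed from the study".
- Section 14.2 runs PFS from study entry to the first scan showing progression. It adds in parentheses that the post-radiotherapy MRI is the baseline for assessing response.

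The reason given in section 12.0 for the new baseline is that this scan "often shows an increased pattern/area of enhancement of indeterminant significance".

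On timing, section 10.0 asks in the adjuvant phase for "Contrast enhanced MRI (including perfusion) after every 2 cycles of therapy", and for scans every 2 to 3 cycles in maintenance. Section 12.0 also says: "All patients will have their tumor measurements recorded at baseline and at the time of each MRI scan". No section mentions the smallest size reached since baseline.

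**The concern.** The stated reason for re-baselining is sound for its purpose: a patient should not be taken off study because of one ambiguous scan. It does not follow that a scan that may be temporarily enlarged should stay the reference for progression on every later scan. If the enhancement fades, or the tumor responds, the reference is left high and later regrowth is measured from the wrong level.

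Take a lesion of 2000 mm² on the post-radiotherapy MRI, then 800 mm², then 2400 mm². It has tripled, but it stands at 120% of baseline. It is not PD, and because section 12.0 makes stable disease the residual category, it counts as stable.

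What is at stake is the date of the PFS event. PFS is the first-listed secondary objective in section 2.0, and section 14.2 also has it computed for the other glioma subtypes. Section 3.2 asks whether maintenance helps to hold a remission, and regrowth of shrunken disease is where this rule is least sensitive.

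**Working it through.** The documents give no figure for PFS timing, so there is none to reproduce. The check uses the protocol's own thresholds and then an illustration over assumed growth rates.

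**Inputs from the protocol.** PD threshold: 25% (12.0). Reference: post-radiotherapy MRI (10.0, 12.0, 14.2). Cycle: 28 days (9.2, 9.3). Adjuvant scans: every 2 cycles, so 2 × 28 = 56 days (8 weeks), and 6 / 2 = 3 scheduled scans. Maintenance scans: every 2 to 3 cycles, so 56 to 84 days (8 to 12 weeks).

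**Growth needed before PD.** Take one lesion and let f be its smallest size divided by its size on the post-radiotherapy MRI. The plan's rule needs growth of 1.25 / f from the smallest size. A smallest-size rule needs 1.25.

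- f = 0.90: 1.25 / 0.90 = 1.39-fold
- f = 0.75: 1.25 / 0.75 = 1.67-fold
- f = 0.50: 1.25 / 0.50 = 2.5-fold
- f = 0.25: 1.25 / 0.25 = 5-fold

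Partial response needs a reduction of at least 50%, so a partial responder with a single lesion has f of 0.50 or less and needs at least 2.5-fold growth. In the example above, PD is called at 1.25 × 2000 = 2500 mm² under the plan's rule, against 1.25 × 800 = 1000 mm². The scan at 2400 mm² falls between (2400 / 2000 = 1.20; 2400 / 800 = 3.0).

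**Delay on scheduled scans.** Let I be the scan interval and T the area doubling time, with growth starting at the smallest-size scan. T is not in the documents, so a range is assumed.

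Delay in scans = ceil(T × log2(1.25 / f) / I) − ceil(T × log2(1.25) / I)

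Delay in weeks for T = 4 / 8 / 16 weeks:

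| Smallest size, % of post-radiotherapy size | 8-week scans | 12-week scans |
|---|---|---|
| 90% | 0 / 0 / 0 | 0 / 0 / 0 |
| 75% | 0 / 0 / 8 | 0 / 0 / 0 |
| 50% | 0 / 8 / 16 | 0 / 0 / 12 |
| 25% | 8 / 16 / 32 | 0 / 12 / 36 |

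For f = 0.50, T = 8, I = 8: 8 × log2(2.5) = 10.6 weeks, seen at scan 2; 8 × log2(1.25) = 2.6 weeks, seen at scan 1. The delay is one scan, or 8 weeks.

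**When the rules can first differ.** At the first follow-up scan the smallest earlier size is the baseline itself, so the rules agree. They can differ from the second follow-up scan on. If only scheduled scans are done, that is after cycle 4. An MRI to confirm a partial response, allowed from 4 weeks after the first, could bring it forward.

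**The case against.** The strongest case on the other side has four parts.

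1. *Late is relative.* Nothing in the documents makes the smallest size the correct reference, and a fixed reference is explicit and reproducible. This is true, and the delay is stated only against a smallest-size rule. But the reason given for the fixed reference does not address regrowth after later shrinkage.

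2. *The reading is an inference.* The PD sentence names no scan, the parenthesis in 14.2 speaks of response, and section 10.0 is written as a removal rule. This too is fair, but section 10.0 says expressly what progression is compared with, and no text points elsewhere. If the sponsor intends another reference for PFS, the plan does not say so.

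3. *Scans and events off schedule.* Confirmation or unscheduled MRIs, 25% growth in another lesion, a new site, death or removal for toxicity can shorten or remove the delay. This stands, so the table is an illustration on scheduled scans only.

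4. *The opposite error.* A 25% rise in a two-dimensional product is about 12% in each diameter (√1.25 = 1.118), or roughly 0.6 mm on a 5 mm lesion. A smallest-size rule will call some small lesions PD through measurement error. This stands as a cost and is why a minimum measurable size is needed.

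Return after complete response is a grey case. Complete response "is the total disappearance of all measurable contrast enhancing tumor on two MRIs separated by at least 4 weeks", and tumor coming back in the same place might or might not be read as a new site.

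**Conclusion.** The concern holds in a limited form. Followed as written, the plan does not call same-site regrowth of a shrunken lesion PD until the lesion is 25% or more above its post-radiotherapy size, so PFS can be dated later than under a smallest-size reference. Over the assumed range the delay runs from 0 to 36 weeks. It is zero in every scenario at 90%, in all but one of six at 75%, and longest with deep shrinkage and slow regrowth. This assumes a single lesion, scheduled scans, steady growth and a patient followed until the threshold is reached. A new site is PD at once, and a lesion that never shrank is judged alike under both rules.

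A reader might infer three stronger things that the documents do not support:

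- *That reported median PFS is inflated by a known amount.* The documents give no response rate, regrowth rate or PFS assumption, so neither the number of patients nor the shift in the median can be computed.
- *That every affected patient loses at least one full scan interval.* Fast regrowth gives no delay, and the events listed under the objection can shorten or remove it.
- *That the trial's decision is compromised.* One-year survival, the Simon rule and the choice between arms (14.1) do not use PD. PFS has no hypothesis or test, and the same rule applies to both arms.

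The change is worth making for a correctly dated secondary endpoint. It does not bear on the primary conclusion.

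**What to change.** In sections 12.0 and 14.2, define progression for PFS as any of:

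- an increase of 25% or more in any measurable lesion over its smallest measurement since, and including, the post-radiotherapy MRI;
- reappearance of measurable enhancing tumor after complete response, where the smallest size is zero and a percentage cannot be used;
- a new site of tumor.

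Fix in advance the minimum size that counts as measurable; section 12.0 gives none. Keep the post-radiotherapy MRI as the reference for response.

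Removal from study can stay tied to the post-radiotherapy MRI, so that measurement error in a small lesion does not end therapy. If so, say in 4.2, 9.3, 10.0 and 13.0 that the removal rule, not the PFS rule, governs starting and stopping adjuvant and maintenance therapy. Otherwise a patient with PD for PFS but not for removal would have unclear eligibility for maintenance, because 4.2 and 9.3 refer only to tumor progression.

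The cost is wording. No new scans are needed: lesions are already measured at each MRI, and because the smallest size never exceeds the baseline size, for lesion growth the PFS rule is met no later than the removal rule. The downsides are somewhat shorter PFS, some early PD calls in small lesions, and two progression rules to apply.

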13.0 CRITERIA FOR REMOVAL FROM STUDY

If at anytime the patient develops progressive disease he/she will be taken off study and referred for alternative therapy.

If at anytime the patient develops unacceptable toxicity he/she will be removed from study.

If at anytime the patient is found to be ineligible for the protocol as designated in the section on Criteria for Patient/Subject Eligibility (i.e., a change in diagnosis), the patient will be removed from the study.

14.2 Secondary endpoints include progression-free survival defined as the date of study entry to the first scan that demonstrates tumor progression (please note that the MRI after completion of radiotherapy will be used as the baseline scan for response assessment). Frequency of toxicity will be tabulated according to the NCI Common Toxicity Criteria (version 3.0). Methylation *MGMT* status will be assessed using real-time PCR. A Fishers exact test will be used to compare one year survival by MGMT status (methylated/unmethylated) in order to observe any trends similar to that from the retrospective EORTC/NCIC.

In addition, these regimens will be administered to forty patients with all other malignant glioma subtypes. Up to twenty patients in each arm will be accrued. Endpoints such as one-year survival probability, overall survival and progression-free survival will be computed in order to gain preliminary data for these other subtypes.

The minimum anticipated sample size would be 66 patients (23 in each cohort plus 20 patients with other malignant glioma subtypes.) If both cohorts accrue patients to the second stage then a total of 118 evaluable patients will be accrued (39 in each cohort + 40 patients with other malignant glioma subtypes). To ensure 118 evaluable patients, we will accrue 140 patients to guard against a 20% rate of ineligibility and patient drop out observed during an interim analysis. Patients who withdraw consent or are found to be ineligible can be replaced. The anticipated rate of accrual is 6 patients/month requiring 12-18 months to complete the accrual to the trial.

14.3 RANDOMIZATION:

Patients will be randomized to dose dense temozolomide or metronomic temozolomide. After eligibility is established and immediately after consent is obtained, patients will be registered in the Protocol Participant Registration (PPR) system and randomized using the Clinical Research Database (CRDB), by calling the MSKCC PPR registry at [contact] between the hours of 8:30 am and 5:30 pm, Monday - Friday. Randomization will be accomplished by the method of random permuted block, and patients will be stratified by KPS (<80 vs \geq 80).

15.0 RESEARCH PARTICIPANT REGISTRATION AND RANDOMIZATION PROCEDURES

Research Participant Registration

15.1 Research Participant Registration

Confirm eligibility as defined in the section entitled Criteria for Patient/Subject Eligibility.

Obtain informed consent, by following procedures defined in section entitled Informed Consent Procedures.

During the registration process registering individuals will be required to complete a protocol specific Eligibility Checklist.

All participants must be registered through the Protocol Participant Registration (PPR) Office at Memorial Sloan-Kettering Cancer Center. PPR is available Monday through Friday from 8:30am – 5:30pm at [contact]. The PPR fax numbers are [contact] and [contact]. Registrations can be phoned in or faxed. The completed signature page of the written consent/verbal script and a completed Eligibility Checklist must be faxed to PPR.

15.2 Randomization

At registration, patients will be randomized to receive either Dose Dense Temozolomide or Metronomic Temozolomide. Each group will receive 6 months of post radiation chemotherapy. Randomization Codes will be generated by the Clinical Research Database (CRDB) in conjunction with the Department of Epidemiology and Biostatistics.

16.0 DATA MANAGEMENT ISSUES

A Research Study Assistant (RSA) will be assigned to the study. The responsibilities of the RSA include project compliance, data collection, abstraction and entry, data reporting, regulatory monitoring, problem resolution and prioritization, and coordinate the activities of the protocol study team.

The data collected for this study will be entered into a secure database. Source documentation will be available to support the computerized patient record.

16.1 Quality Assurance

Weekly registration reports will be generated to monitor patient accruals and completeness of registration data. Routine data quality reports will be generated to assess missing data and inconsistencies. Accrual rates and extext and accuracy of evaluations and follow-up will be monitored periodically throughout the study period and potential problems will be brought to the attention of the study team for discussion and action

Random-sample data quality and protocol compliance audits will be conducted by the study team, at a minimum of two times per year, more frequently if indicated.

16.2 Data and Safety Monitoring

The Data and Safety Monitoring (DSM) Plans at Memorial Sloan-Kettering Cancer Center were approved by the National Cancer Institute in September 2001. The plans address the new policies set forth by the NCI in the document entitled "Policy of the National Cancer Institute for Data and Safety Monitoring of Clinical Trials" which can be found at: http://cancertrials.nci.nih.gov/researchers/dsm/index.html. The DSM Plans at MSKCC were established and are monitored by the Office of Clinical Research. The MSKCC Data and Safety Monitoring Plans can be found on the MSKCC Intranet at: http://mskweb2.mskcc.org/irb/index.htm

IRB#: 05-079A(17)

There are several different mechanisms by which clinical trials are monitored for data, safety and quality. There are institutional processes in place for quality assurance (e.g., protocol monitoring, compliance and data verification audits, therapeutic response, and staff education on clinical research QA) and departmental procedures for quality control, plus there are two institutional committees that are responsible for monitoring the activities of our clinical trials programs. The committees: *Data and Safety Monitoring Committee (DSMC)* for Phase I and II clinical trials, and the *Data and Safety Monitoring Board (DSMB)* for Phase III clinical trials, report to the Center's Research Council and Institutional Review Board.

During the protocol development and review process, each protocol will be assessed for its level of risk and degree of monitoring required. Every type of protocol (e.g., NIH sponsored, in-house sponsored, industrial sponsored, NCI cooperative group, etc.) will be addressed and the monitoring procedures will be established at the time of protocol activation.

17.0 PROTECTION OF HUMAN SUBJECTS

17.1 Privacy

MSKCC's Privacy Office may allow the use and disclosure of protected health information pursuant to a completed and signed Research Authorization form. The use and disclosure of protected health information will be limited to the individuals described in the Research Authorization form. A Research Authorization form must be completed by the Principal Investigator and approved by the IRB and Privacy Board.

17.2 Serious Adverse Event (SAE) Reporting

Any SAE must be reported to the IRB/PB as soon as possible but no later than 5 calendar days. The IRB/PB requires a Clinical Research Database (CRDB) SAE report be submitted electronically to the SAE Office at [contact] containing the following information:

Fields populated from the CRDB:

- Subject's name (generate the report with only initials if it will be sent outside of MSKCC)
- Medical record number
- Disease/histology (if applicable)
- Protocol number and title

Data needing to be entered:

- The date the adverse event occurred
- The adverse event
- •Relationship of the adverse event to the treatment (drug, device, or intervention)

IRB#: 05-079A(17)

- If the AE was expected
- The severity of the AE
- The intervention
- Detailed text that includes the following information:
 - A explanation of how the AE was handled
 - A description of the subject's condition
 - Indication if the subject remains on the study
 - If an amendment will need to be made to the protocol and/or consent form

The PI's signature and the date it was signed are required on the completed report.

18.0 INFORMED CONSENT PROCEDURES

Before protocol-specified procedures are carried out, consenting professionals will explain full details of the protocol and study procedures as well as the risks involved to participants prior to their inclusion in the study. Participants will also be informed that they are free to withdraw from the study at any time. All participants must sign an IRB/PB-approved consent form indicating their consent to participate. This consent form meets the requirements of the Code of Federal Regulations and the Institutional Review Board/Privacy Board of this Center. The consent form will include the following:

- 1. The nature and objectives, potential risks and benefits of the intended study.
- 2. The length of study and the likely follow-up required.
- 3. Alternatives to the proposed study. (This will include available standard and investigational therapies. In addition, patients will be offered an option of supportive care for therapeutic studies.)
- 4. The name of the investigator(s) responsible for the protocol.
- 5. The right of the participant to accept or refuse study interventions/interactions and to withdraw from participation at any time.

Before any protocol-specific procedures can be carried out, the consenting professional will fully explain the aspects of patient privacy concerning research specific information.

In addition to signing the IRB Informed Consent, all patients must agree to the Research Authorization component of the informed consent form.

Each participant and consenting professional will sign the consent form. The participant must receive a copy of the signed informed consent form.

20.0 APPENDICES
